2.0 OBJECTIVES

Our hypothesis is that change in ¹⁸F-FFNP uptake following 1-day of estradiol is a strong predictor of response to ET in patients with hormone-sensitive (ER⁺/± PgR⁺)/HER2- breast cancer. We believe the increase in tumor PgR after 1-day estradiol will be more reliable than a decrease after estrogen deprivation, particularly because most breast cancer patients are postmenopausal and basal PgR levels will be low due to the low endogenous, menopausal estrogen levels. Thus, we propose to use a hormone-challenge test for assessment of functional

ER based on the change in ^{18}F -FFNP uptake before and after a 1-day estradiol challenge in patients with ER+ metastatic breast cancer. We expect that the changes in ^{18}F -FFNP uptake to be a highly reliable means to predict a favorable response of ER+ breast cancer to ET. We propose to study patients with biopsy-proven new diagnosis of ER+ metastatic/recurrent breast cancer who are going to be treated with ET (tamoxifen, AI agents or faslodex) according to standard of care.

2.1. Evaluate whether the change in tumor uptake of ^{18}F -FFNP following a 1-day estradiol challenge differs among patients who respond to ET versus those who do not respond.

2.1.1 Determine the optimum cutoff value for change in tumor ^{18}F -FFNP uptake after estradiol to distinguish responders from nonresponders.

2.1.2 Evaluate whether the change in tumor uptake of FFNP can identify patients with hormone-sensitive disease who will respond to ET with greater sensitivity and selectivity than tumor PgR measured by IHC.

2.2 Evaluate the heterogeneity of tumor ^{18}F -FFNP uptake at baseline and after estradiol challenge in patients with multiple metastatic foci.

2.2.1. Explore whether response is related to ^{18}F -FFNP uptake heterogeneity. To assess the heterogeneity at the baseline, a comparison with FDG-PET/CT will be performed to map the metabolically active disease. Once the metabolically active disease is determined, FDG+/FFNP- will be considered as discordant lesions. At follow-up, the baseline FFNP-PET/CT will be correlated with follow-up FFNP-PET/CT to assess heterogeneity in response to estradiol.

3.0 PATIENT SELECTION

3.1 Inclusion Criteria

1. Patient must be postmenopausal defined as meeting one or more of the following:
 - a. Age \geq 60 years
 - b. Amenorrheic for at least 12 months
 - c. Surgically sterile- having undergone bilateral oophorectomy,
 - d. FSH laboratory test level in postmenopausal range according to institutional standards (note FSH lab test must be ordered as standard of care to determine best treatment option and should not be ordered simply to confirm eligibility to this study)

- e. OR Pre-menopausal for whom standard ET is planned with ovarian suppression (imaging on study should be completed prior to start of ovarian suppression)
- 2. Patient must have histological or cytological confirmed breast cancer and fall into one of the following categories:
 - a. New diagnosis with plans for at least 6 months of neoadjuvant ET or any amount of neoadjuvant ET if surgery is planned as this will be used for response assessment .
 - b. Patients with newly diagnosed metastatic breast cancer or patient with known metastatic disease who has progressed while on therapy (no washout period is needed if the patient was treated with AIs or chemotherapy, but 2 months washout period is needed if the patient was treated with tamoxifen) who are going to be treated with ET.
- 3. Patient must have any one of the following types of breast cancer (primary or metastatic): ER+/PgR+/HER2– or ER+/PgR–/HER2–.
 - a. ER+ is defined as Allred score of at least 4 and greater.
 - b. PgR+ is defined as Allred score of at least 4 and greater.
 - c. IHC is the primary assay methodology for HER2. HER2– refers to HER2 of 0, 1+ by IHC or negative by fluorescence in situ hybridization (FISH)
- 4. Patient must have at least one measurable lesion according to RECIST 1.1 by radiological evaluation (ultrasound, mammography, MRI, CT, PET) or physical examination.
 - a. Patients with evaluable osseous metastasis that are lytic or mixed lytic-sclerotic are eligible.
 - b. Patients with hepatic lesions may be eligible provided the location of the lesion is peripheral or not too close to hepatic ducts. Decision on hepatic lesion eligibility will be made by the principal investigator or sub-investigator after careful review of all available imaging to ensure evaluation of the lesion will not be obscured by normal hepatobiliary excretion of ¹⁸F-FFNP.
- 5. Patient must be able to understand and willing to sign a written informed consent document.
- 6. Prior chemotherapy or endocrine therapy is allowed
- 7. The patient must have an ECOG performance status of 0-2 or, based on the judgment of the treating medical oncologist, can tolerate imaging and at least 6 months of ET
- 8. The patient should have a life expectancy of > 6 months.

3.2 Exclusion Criteria

- 1. Patient with other invasive malignancies, with the exception of non-melanoma skin cancer or cervical carcinoma in-situ, who had (or have) any evidence of the other cancer present within the last 5 years
- 2. Unable to tolerate up to 60 min of PET imaging per imaging session.
- 3. Patients with non-measurable non-evaluable lesions such as pleural effusion are not eligible to participate.

4. Patients with vertebral lesions that, in the opinion of the Principal Investigator and the treating medical oncologist, pose an imminent risk for cord compression.

3.3 Inclusion of Men and Minorities

Because breast cancer occurs most often in women, and the receptor status of breast cancer in women has been studied more often, men will not be eligible for this trial. The trial is open to members of all races and ethnic groups and participation will be encouraged.

4.0 PATIENT REGISTRATION

Patients must not start any protocol intervention prior to registration through the Siteman Cancer Center.

The following steps must be taken before registering patients to this study:

1. Confirmation of patient eligibility
2. Registration of patient in the Siteman Cancer Center database
3. Assignment of unique patient number (UPN)

4.1 Confirmation of Patient Eligibility

Confirm patient eligibility collecting the information listed below:

1. The registering MD's name
2. Patient's race, sex, and DOB
3. Three letters (or two letters and a dash) for the patient's initials
4. Copy of signed consent form
5. Completed eligibility checklist, signed and dated by a member of the study team
6. Copy of appropriate source documentation confirming patient eligibility

4.2 Patient Registration in the Siteman Cancer Center Database

All patients must be registered through the Siteman Cancer Center database.

4.3 Assignment of UPN

Each patient will be identified with a unique patient number (UPN) for this study. Patients will also be identified by first, middle, and last initials. If the patient has no middle initial, a dash will be used on the case report forms (CRFs). All data will be recorded with this identification number on the appropriate CRFs.

5.0 METHODS

5.1 Study Design

A single center, open-label, baseline controlled diagnostic imaging study designed to assess the predictive value of ^{18}F -FFNP-PET/CT imaging women who complete an estradiol challenge test.

5.2 Patient Population

Fifty postmenopausal women OR Pre-menopausal for whom standard ET is planned with ovarian suppression (imaging on study should be completed prior to start of ovarian suppression) with newly diagnosed, metastatic or recurrent breast cancer which is ER+ disease (ER+/PgR+/HER2-, ER+/PgR-/HER2-) will undergo one FDG PET/CT scan to map the metabolically active disease plus two ^{18}F -FFNP-PET/CT; one prior to estradiol challenge test and a second one immediately following one day of estradiol challenge test (2 mg tid). All scans will be completed prior to the start of standard of care ET. Patients who have had an FDG-PET/CT scan (or other functional studies such as bone scan in patients with bone dominant disease or a contrast CT scan for hepatic dominant disease) done within 8 weeks of study entry may not need to repeat the scan at the discretion of the Principal Investigator and Co-Investigator Medical oncologists. Any subject whose imaging is deemed not evaluable for any reason or any subject who does not complete both FFNP-PET/CT imaging sessions for any reason may be replaced on study. The study ID assigned to the subject being replaced will not be re-used.

5.3 Estradiol Challenge Test

The estradiol challenge test will consist of administering a total of 6 mg of estradiol dosed orally as three 2 mg tablets with each tablet being administered approximately 8 hours apart and within a 24 hour period. This estradiol medication will be provided to the patient by the study. Dosing will be such that the third dose of estradiol will be administered at a minimum 8 hours (8 ± 2 hours) and a maximum 48 hours prior to the scheduled injection of ^{18}F -FFNP for the repeat ^{18}F -FFNP-PET/CT imaging session. Timing of the estradiol administration is critical so that the effect of estradiol will be captured within the imaging session. The first dose of estradiol can be administered as soon as immediately following the baseline ^{18}F -FFNP-PET/CT imaging session with the post estradiol ^{18}F -FFNP -PET/CT imaging session being scheduled for the following day. No more than a maximum of 4 weeks should occur between the baseline and the post estradiol challenge ^{18}F -FFNP -PET/CT imaging sessions. A subject specific calendar will be given to each participant that includes dates and times for estradiol administration and follow up ^{18}F -FFNP-PET/CT imaging session. Whenever possible, blood will be obtained for measurement of the serum estradiol level, using a high-sensitivity radioimmunoassay (Herting MM. BJ. Cereb Cortex. 2012 Sep;22(9):1979-92) before injection of ^{18}F -FFNP at the baseline and after estradiol challenge before the 2nd ^{18}F -FFNP injection to document that it increased appropriately.

5.4 Risks Related to Estradiol Challenge Test.

Side effects from taking a total 6 mg of estradiol over a 24 hour period are expected to be minimal. Subjects may experience nausea from a dose this small. When estradiol is administered in much higher doses as therapy and given daily over a longer period of time the following side effects have been reported: nausea and or vomiting; bone pain, breast tenderness and/or enlargement; vaginal bleeding, tiredness, changes in skin color; insomnia (difficulty falling or staying asleep); yeast infections, increase or decrease in vaginal secretions, and headaches

6.0 IMAGING PARAMETERS AND ANALYSIS

All research imaging studies will be performed using the CTI/Siemens Biograph 40 PET/CT scanner. The Biograph 40 is a 4-ring PET scanner made up of a multi-LSO-detector ring system with 3D acquisition and reconstruction and 109 image planes with an extended 21.6 cm axial field of view, enabling the detection of 78% more photons (compared with a conventional-field-of-view scanner). The scanner features high resolution (less than 5mm in transaxial and axial dimensions) with Pico 3D ultra-fast electronic for decreased dead-time and high signal-to-noise ratio.

All patients will undergo routine clinical staging as dictated by the treating medical oncologist or surgeon. The results of the PET studies will not be provided to the patient or the treating oncologist unless the CT images demonstrate an unsuspected, potentially life-threatening abnormality that warrants further investigation and/or urgent therapy (e.g., a mass impinging on the spinal cord seen on the CT images).

If performed for research purposes, the results of the ^{18}F -FDG-PET/CT scan will be fully interpreted and reported to the medical record following the same procedures as if done as a standard of care examination.

6.1 Drug Preparation

6.1.1 ^{18}F -FFNP

^{18}F -FFNP will be prepared using an adaptation of a published procedure (Buckman BO J Med Chem. 1995;38(2):328-37; Kym PR J Med Chem. 1993;36(9):1111-9 ; Vijaykumar D J Org Chem. 2002;67(14):4904-10) . The diastereomerically pure 21-mesylate, endo-9a precursor was reacted with non-resin-treated [^{18}F]-fluoride, Kryptofix222 (Aldrich), and potassium carbonate in acetonitrile at 85C for 5 min. The reaction mixture was prepurified by passing through a silica light SepPak (Waters), followed by reversed-phase high-performance liquid chromatography purification. ^{18}F -FFNP was extracted from the high-performance liquid chromatography mobile phase using solid-phase extraction and was reconstituted in 10% ethanol in saline. Starting from 11.1 GBq (300 mCi) of ^{18}F fluoride and using 0.4 mg of potassium carbonate and prompt work-up to avoid the decomposition of the acid- and base-labile ^{18}F -FFNP, we

produced 0.74–1.11 GBq (20–30 mCi) of ^{18}F -FFNP at the end of synthesis (90 min). The final formulation of ^{18}F -FFNP is stabilized in ethanol or saline. Non-resin-treated ^{18}F -fluoride was used to achieve high specific activity. The specific activity was measured by high-performance liquid chromatography to be 185–740 GBq (5,000–20,000 mCi)/ μmol , and the effective specific activity was measured by receptor binding assay to be up to 740 GBq (20,000 mCi)/ μmol .

6.1.2 ^{18}F -FDG

FDG will be prepared and distributed under the Washington University Cyclotron Facility's ANDA for FDG.

6.2 ^{18}F -FDG-PET/CT Imaging Parameters

If performed for research purposes, subjects will undergo standard oncologic ^{18}F -FDG-PET/CT imaging that includes the base of the skull to upper thighs (or extended to include metastatic disease in the lower legs, or possible brain metastasis, if applicable) imaging.

Subjects will be asked to fast for a minimum of 4 hours with only plain water to drink during the fasting period. On the day of the scheduled scan a small IV catheter will be placed in an upper extremity arm vein (preferably contralateral to the patient's breast cancer) to allow for injection of FDG. Prior to injection a small sample of blood (less than 1 teaspoon) will be obtained for glucose measurement. Injection of FDG will proceed if blood glucose, if 200 mg/dL or less or with approval of the PI or nuclear medicine co-investigator (authorized user), if blood glucose is greater than 200 mg/dL.

FDG dose will be based upon weight according to the standard nuclear medicine imaging protocol with the average dose injected 15 mCi. Imaging will occur 50-70 minutes post FDG injection. Subjects should be asked to rest and remain quiet, comfortable, and warm during the uptake phase. To avoid brown fat uptake the use of warm blankets is encouraged. IV or oral hydration (up to 500 ml unless subject has known fluid restrictions) is also encouraged during the uptake period.

Immediately prior to imaging, subjects will be asked to empty the bladder in the restroom. The subject will be placed supine on the imaging table with arms resting above the head or secured comfortably by the side of the body. A spiral CT scan for attenuation correction will be obtained from the skull through the upper thighs. The CT will consist of a 10-20 second topogram for determining correct anatomical positioning followed by a spiral CT at a maximum of 50 mAS. Care dose will be calculated for each scan and the care dose imaging parameters will be used if less than the maximum 50 mAs is calculated. CT imaging will be acquired with a standard 120 kVp. Average spiral CT scan time is 15-30 seconds. Scans are acquired using a 5 mm slice thickness.

Immediately after the attenuation CT scan and approximately 30 minutes after injection of FFNP, emission imaging will be obtained (2-5 minutes per bed position adjusted as needed based on subject height, weight, and injected dose).

6.3 ^{18}F -FFNP-PET/CT Imaging Parameters

^{18}F -FFNP-PET body imaging will include the base of the skull to upper thighs (or extended to include metastatic disease in the lower legs, or possible brain metastasis as applicable) imaging. Site of scan can also be modified based on information obtained from FDG-PET/CT imaging.

There are no eating or drinking restrictions for ^{18}F -FFNP-PET imaging. On the day of the scheduled scan a small IV catheter will be placed in an upper extremity arm vein (preferably contralateral to the patient's breast cancer) to allow for injection of ^{18}F -FFNP. NOTE: FFNP is sticky and injection through port-a cath or extended amounts of IV tubing should be avoided whenever possible. Baseline vital signs consisting of blood pressure, heart rate, breathing rate and temperature will be obtained prior to the injection of ^{18}F -FFNP. A maximum dose 10 mCi (dose range 7-10 mCi) of ^{18}F -FFNP will be injected into the established IV line. The dose will be followed with a normal saline flush of 10-30 ml. Subjects will be asked to rest comfortably in the injection room for approximately 30-40 minutes while ^{18}F -FFNP circulates in the body (warm blankets and oral hydration is encouraged). Approximately 10-30 minutes after injection and during this resting period vital signs will be taken to assess for any post injection changes.

Immediately prior to imaging, subjects will be asked to empty the bladder in the restroom. The subject will be placed supine on the imaging table with arms resting above the head or secured comfortably by the side of the body. A spiral CT scan for attenuation correction will be obtained from the skull through the upper thighs. The CT will consist of a 10-20 second topogram for determining correct anatomical positioning followed by a spiral CT at a maximum of 50 mAS. Care dose will be calculated for each scan and the care dose imaging parameters will be used if less than the maximum 50 mAs is calculated. CT imaging will be acquired with a standard 120 kVp. Average spiral CT scan time is 15-30 seconds. Scans are acquired using a 5 mm slice thickness. Immediately after the attenuation CT scan and approximately 30 minutes after injection of FFNP, emission imaging will be obtained (2-5 minutes per bed position adjusted as needed based on subject height, weight, and injected dose). The ^{18}F -FFNP dose and the scans parameters will be kept as close as possible for both ^{18}F -FFNP-PET/CT scans in each patient.

At the end of the imaging session, subjects will be encouraged to void and post imaging vital signs will be assessed prior to discharge.

6.4 Vital Sign Assessments

All vital signs will be recorded on the case report form. Vital signs may be obtained with the subject in the supine or upright position. Care will be taken to obtain subsequent recordings with the subject in the same position (supine or upright). Although allergic or other immediate adverse reactions are not anticipated, subjects will be monitored for at least 30 min post injection in an area where emergency equipment is available. Vital signs will be obtained pre-injection, within 30 min post injection, and at the completion of each imaging session. Vital signs will include the following: heart rate, systolic blood pressure, diastolic blood pressure, respiratory rate, and body temperature. Changes in vital sign assessment will be determined separately at each imaging session and considered noteworthy if they fall outside of normal range and / or the subject is symptomatic: Subjects whose baseline ranges start outside of normal range will be assessed if they are symptomatic and / or meet criteria for assessment due to change in readings as noted in table below. The following changes from baseline will be considered noteworthy:

Observation	Normal Range	Change for Assessment
Heart rate	50 – 110 beats/min	> 30 beats per minute
Systolic Blood Pressure	80-140 mm Hg	> 30 mm Hg
Diastolic Blood Pressure	60-90 mm Hg	> 20 mm Hg

Heart rate: > 30 beats per minute
Systolic blood pressure > 30 mm Hg
Diastolic blood pressure > 20 mm Hg

Noteworthy changes will be documented on the Case Report Forms (CRF). The Principal Investigator will indicate on the CRF whether or not the changes in vital signs are clinically significant. If clinically significant, the principal investigator will assess the causality of the change to the injection of ¹⁸F-FFNP or PET/CT imaging. Clinically significant changes in vital signs will be followed as needed until they return to baseline or normal levels, or until follow-up is no longer warranted. If a clinically significant change of a vital sign is noted, it will be reported on the adverse event log.

6.5 Image Analysis

The emission images will be corrected for measured attenuation using CT data according to the provide scanner manufacturer software package. FDG-PET/CT images will be evaluated and reported according to standard of care imaging procedures.

FFNP-PET/CT images will be evaluated by one observer qualitatively. PET images also will be evaluated semiquantitatively with the knowledge of the location of the lesion(s) by the use of the standardized uptake value (SUV) and tumor-to-normal tissue (T/N)

ratio. The SUV is widely used for assessment of regional tracer accumulation in oncological studies, is technically simple to perform, and makes imaging easier for the patient because longer dynamic imaging is not required. SUV is a decay-corrected measurement of activity per volume of tissue (nCi/mL) divided by the average activity per unit mass in the entire body. The absolute change and the percent change in uptake of ^{18}F -FFNP will be assessed semiquantitatively and correlated with the clinical and radiologic results and subsequently with the results of the clinical follow-up evaluation. In patients with multiple lesions, the uptake up to 5 most intense lesions seen on PET images will be determined and the overall average values for all of the known lesions also will be recorded. The changes in SUV and T/N between the baseline and post estradiol challenge FFNP-PET/CT images will be compared in responders and nonresponders. Volumes of interest (VOIs) will be drawn around the entire lesion with the knowledge of the location of the tumor. SUV_{max} will be determined within the VOI. In addition, a similar volume of interest will be drawn in a comparable normal tissue region. The T/N ratio will be calculated by dividing the SUV_{max} of the tumor by the average SUV of normal comparable tissue. The absolute change and the percent change in uptake of ^{18}F -FFNP will be assessed semi-quantitatively and correlated with the clinical and radiologic results and subsequently with the results of the clinical follow-up evaluation. In patients with multiple lesions, the uptake of up to 5 lesions, selected as the most intense lesions seen on PET, will be determined and the overall average values for all of the known lesions also will be recorded. In addition, in patients with multiple lesions, SUV_{max} and T/N ratio will be measured for all known measurable lesions to assess within-patient heterogeneity in ^{18}F -FFNP uptake. Considering the optimum cutoff value for ^{18}F -FFNP uptake that distinguishes responders from nonresponders, lesions will be classified as ^{18}F -FFNP+ for lesions with ^{18}F -FFNP uptake at or greater than the cutoff value and ^{18}F -FFNP- for lesions with ^{18}F -FFNP uptake below the cutoff value. The changes in SUV and T/N after treatment will be compared in responders and nonresponders. The results of the PET studies will not be provided to the patient or the treating oncologist (see above). Clinical follow-up will provide information on tumor response, which will then be correlated with the sequential PET results to determine if these are predictive of ultimate response to estrogen therapy.

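### Baseline FFNP heterogeneity is read from SUVmax and SUVmax-based T/N with no allowance for lesion size, so part of the spread between lesions can be size and not PgR

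*Combined protocol and SAP*

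**What the plan says.** Section 6.5 defines the lesion measurement: "Volumes of interest (VOIs) will be drawn around the entire lesion with the knowledge of the location of the tumor". SUVmax is taken inside that volume, and T/N is formed by "dividing the SUV_{max} of the tumor by the average SUV of normal comparable tissue". The numerator is therefore a maximum and the denominator a mean. In patients with multiple lesions, SUVmax and the "T/N ratio will be measured for all known measurable lesions to assess within-patient heterogeneity in" FFNP uptake. Each lesion is then labelled FFNP+ or FFNP- at a single cutoff.

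On image quality:

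- Section 6.5: "The emission images will be corrected for measured attenuation using CT data". No partial-volume or recovery correction is stated.
- Section 6.0: "high resolution (less than 5mm in transaxial and axial dimensions"). No voxel noise level is given.
- Section 6.3: emission time is "2-5 minutes per bed position adjusted as needed based on subject height, weight, and injected dose", so noise can differ between patients.

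Section 2.2.1 counts a lesion as discordant at baseline if it is FDG-positive and FFNP-negative. It judges heterogeneity after estradiol by comparing the two FFNP scans. Section 10.1 describes no heterogeneity analysis.

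**The concern.** Two mechanisms make the reading depend on lesion size when true uptake does not:

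- Limited resolution spreads signal out of a small lesion and lowers its peak.
- The highest of many noisy voxels exceeds the highest of a few, so a large lesion reads high.

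Both push the same way. Dividing by a normal-tissue mean does not remove either, because that mean carries neither error.

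Section 1.2 interprets this kind of heterogeneity as receptor expression, and objective 2.2.1 asks whether it relates to response. If part of the baseline spread comes from size, the heterogeneity finding is partly about lesion dimensions. Some lesions near an absolute-uptake cutoff would also change label without any difference in PgR.

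**Working it through.** **The plan's own figure.** The only design calculation is the detectable difference for the primary comparison (Section 10.1). A two-sided two-sample t-test at 80% power gives 1.011 SD for 10 v 40 and 0.809 SD for 25 v 25, matching the stated 101% and 80.9% of an SD. It does not bear on heterogeneity, for which the plan gives no figure.

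**Inputs.**

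- From the documents: whole-lesion volume, SUVmax, mean denominator, attenuation correction only, resolution below 5 mm.
- Assumed: effective resolution (FWHM, F) of 5-6 mm, with 7 mm as a variant; voxel noise CV of 5-15%; uniform spherical lesions; diameters D from 10 to 40 mm. Section 3.1 ties measurability to RECIST 1.1 but gives no millimetre value, so 10 mm is an assumption.

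**Step 1: blur alone.** With R = D/2 and s = F/2.355, the recovery at the centre of a sphere is

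RC = erf(R/(s√2)) − √(2/π) × (R/s) × exp(−R²/(2s²)),

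and the measured T/N is 1 + RC × (true T/N − 1).

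For F = 5 and D = 10: s = 2.123 and R/s = 2.355, so RC = 0.981 − 0.117 = 0.864. A true T/N of 2 reads 1.864. A 40 mm lesion has RC = 1.000 and reads 2.000, so the ratio is 2.000/1.864 = 1.07.

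| F (mm) | RC at 10 mm | RC at 15 mm | 40 v 10 mm | 40 v 15 mm |
|---|---|---|---|---|
| 5 | 0.864 | 0.994 | 2/1.864 = 1.07 | 2/1.994 = 1.00 |
| 6 | 0.722 | 0.966 | 2/1.722 = 1.16 | 2/1.966 = 1.02 |
| 7 | 0.581 | 0.905 | 2/1.581 = 1.27 | 2/1.905 = 1.05 |

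At the stated resolution bound, blur is a modest effect at 10 mm and essentially nil from 15 mm.

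**Step 2: add noise.** Monte Carlo: the blurred sphere is multiplied by noise smoothed to the same FWHM, and the maximum is taken within the lesion. For a true T/N of 2:

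| F (mm) | Noise CV | 40 v 10 mm |
|---|---|---|
| 5 | 5% | about 1.25 |
| 5 | 10-15% | 1.37-1.46 |
| 6 | 10-15% | 1.47-1.58 |

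For 40 v 15 mm the ratio is 1.11 at F = 5 with 5% noise, and 1.18-1.28 at F = 5-6 with 10-15% noise. For 40 v 20 mm it is 1.09-1.16 at 10-15% noise. The noise part therefore persists in lesions that blur hardly touches.

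**Step 3: a lesion with no specific uptake (true T/N of 1).** At F = 5-6 and 10-15% noise it reads 1.15-1.26 at 10 mm and 1.33-1.51 at 40 mm. The mean denominator does not cancel the error.

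**Step 4: other contrast and resolution.** At a true ratio of 4 with 5-15% noise, 40 v 10 mm gives 1.23-1.46 at F = 5 and 1.53-1.83 at F = 7.

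**Step 5: change within a lesion.** Take F = 7, background 1, and lesion uptake rising from 4 to 6 (true +50%), without noise. At 10 mm: (1 + 0.581 × 5)/(1 + 0.581 × 3) = 3.905/2.743, or +42%. At 15 mm it is +49%, and at 30 mm +50%. The size effect mostly cancels. Section 6.3 also asks that tracer dose and scan settings be kept close across a patient's two FFNP scans, which helps the noise part cancel.

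**The case against.** The strongest case against acting has five parts.

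- **Size range.** A reader might infer that lesions of any size are compared. The text says measurable lesions, with RECIST 1.1 as the standard, so the smallest are out. This stands. Section 3.1 does admit bone lesions that are only evaluable, and Section 6.5 does not say how they are handled.
- **Assumed noise.** The documents give no noise level, and ratios near 1.6 need 6 mm resolution, 15% noise and the extreme size pair. This stands, which is why the result is given as a range with the 15 mm comparison beside it. Under the assumed noise of 5% or more the direction does not change.
- **Size as the explanation.** A reader might infer that reported heterogeneity would be mainly lesion size. The documents do not support that. Section 1.2 cites a study with an 8.2-fold difference in uptake between lesions of one patient. That was FES, a different tracer, but it is far above the artefact found here.
- **The cutoff.** Sections 2.1.1 and 10.1 derive a cutoff only for change after estradiol, while Section 6.5 words the lesion cutoff as uptake. If the change cutoff is meant, size-driven FFNP- labels largely disappear. This stands, and the plan should settle it.
- **Link with response.** A reader might infer that size spread follows tumour burden and so creates a false association with response. No passage supports that chain, and the plan defines no patient-level heterogeneity score through which it could be measured. It remains a possibility only.

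**Conclusion.** The concern holds in a limited form. Followed as written, Section 6.5 lets lesion size enter the baseline comparison of FFNP uptake between lesions, always in favour of larger lesions. At identical true T/N of 2, the effect is about 1.25-1.6-fold for 40 v 10 mm and 1.1-1.3-fold for 40 v 15 mm. That is enough to move labels near an absolute-uptake cutoff. These figures rest on assumed resolution of 5-6 mm, 5-15% noise and spherical lesions; the documents supply only the bound of less than 5 mm.

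The primary comparison uses change after estradiol and is largely untouched, and its power calculation is unaffected. Objective 2.2.1 is exploratory and the study calls itself a pilot. This is a worthwhile addition to the analysis and not a threat to the main result.

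**What to change.** In Sections 6.5 and 10.1:

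1. Record each lesion's diameter from CT already acquired. The attenuation CT is limited to 50 mAs with 5 mm slices (Section 6.3), so use a diagnostic CT where it cannot size the lesion.
2. Keep the planned baseline heterogeneity analysis. Beside it, report a lesion-level mixed model of log uptake on log diameter with a patient random intercept.
3. Add a sensitivity analysis of the FFNP+/- counts and the FDG+/FFNP- discordance counts, restricted to lesions of at least about 15-20 mm. This removes most of the blur effect but not all of the noise effect, so it complements item 2 and does not replace it.
4. Judge heterogeneity after estradiol on each lesion's own percent change.
5. State whether the FFNP+/- cutoff applies to uptake or to change.

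The cost is one diameter per lesion and some analysis wording, with no added scan and no change in sample size. Fewer lesions enter the restricted counts. Adjusting for diameter may also remove real differences in PgR that go with size, which is why the unadjusted result stays in the report.
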